8.5 Safety Variables and Analysis

8.5.1 Safety Variables

The safety and tolerability of abemaciclib treatment will be assessed throughout the study by evaluating AEs.

8.5.2 Safety Analysis

The safety analysis set will be used for all safety analyses.

All AEs will be graded by CTCAE v 5.0. Summaries will be presented for all AEs (overall and by severity), AEs determined by the investigator to be related or not related to study treatment (overall and by severity), SAEs, serious treatment-related AEs, AEs leading to withdrawal, and Grade 3 and 4 AEs. Participant listings of AEs, SAEs, Grade 3 and 4 AEs, and AEs leading to withdrawal will be presented.

The number and percentage of participants with Grade 3 or 4 values will be tabulated. Summaries of laboratory values for laboratory parameters will be completed as applicable. Vital signs abnormalities will be categorized and tabulated. Summaries of the vital signs measurements will be provided.

The use of concomitant medications will be summarized by therapeutic class using descriptive statistics. Concomitant medications will include all medications taken while the participant is treated with study drug.

For continuous variables, descriptive statistics (n, mean, standard deviation, standard error, median, minimum, and maximum) will be provided for actual values and changes from baseline to each time point. For categorical variables, participant counts and percentages will be provided. Descriptive summaries of SAEs, participant withdrawals due to AEs, and potentially clinically significant abnormal values (clinical laboratory or vital signs) based on predefined criteria will also be provided.

If any participant dies during the study, a listing of deaths will be provided and all relevant information will be discussed in the participant narrative.

8.6 Safety Analysis

The data safety monitoring committee (DSMC) will review all safety data following recruitment of the 5 subjects. If the DSMC requests earlier views of the safety data, the appropriate data will be cleaned and provided. The study may be terminated early if unexpected toxicities are observed, but this should be unanticipated. No interim analyses are planned for this pilot study.

9.0 CONFIDENTIALITY, PRIVACY, AND DATA MANAGEMENT

The Principal Investigator will strictly adhere to the research data security and integrity plan put forth in the following Penn State Health Institutional policy "HRP-598 – Research Data Plan Review Form".

9.1 Patient Identifiers associated with data and/or specimens

Participants will be identified in all reports using a protocol specific unique patient identification number. A Master list linking these unique identification numbers and the participant is maintained in the limited access, password protected Cancer Institute OnCore Clinical Trials Management System (CTMS).

9.2 Data Storage

Data will be maintained in the OnCore CTMS per institutional requirements for data access and security. OnCore is a limited access, password protected system maintained in the Cancer Institute.

All data will be retained in the CTMS until the time period required by the FDA and institutional IRB. Data destruction will be completed according to institutional policies.

10.0 ASSESSMENT OF SAFETY AND ADVERSE EVENT REPORTING

In this study, safety will be assessed by the PI by evaluating results of assessments including but not limited to verbal inquiries, physical examinations, clinical laboratory test results, vital signs measurements, ECG findings, and concomitant medication usage.

10.1 Adverse Events

10.1.1 Definition of an AE

An AE is any untoward medical occurrence in a participant administered a pharmaceutical product, regardless of whether it has a causal relationship with this treatment.

An AE can, therefore, be any unfavorable and unintended physical sign, symptom, or laboratory parameter that develops or worsens in severity during the course of the study, or significant worsening of the disease under study or of any concurrent disease, whether or not considered related to the study drug. A new condition or the worsening of a pre-existing condition will be considered an AE. Stable chronic conditions (such as arthritis) that are present before the participant signs the informed consent form and do not worsen during the study will not be considered AEs.

Accordingly, an AE can include any of the following:

- Intercurrent illnesses
- Physical injuries
- Events possibly related to concomitant medication
- Significant worsening (change in nature, severity, or frequency) of the disease under study or other pre-existing conditions. (Note: A condition recorded as pre-existing that is intermittently symptomatic [e.g., headache] and which occurs during the study should be recorded as an AE.)
- Drug interactions
- Events occurring during diagnostic procedures
- Laboratory or diagnostic test abnormalities that result in the withdrawal of the participant from the study, are associated with clinical signs and symptoms or an SAE, or require medical treatment or further diagnostic work-up, or are considered by the Principal Investigator to be clinically significant. Note: Abnormal laboratory test results at the screening visit that preclude a participant from entering the study or receiving study treatment are not considered AEs, but will be evaluated to monitor data from participants who do not meet screening criteria.
- All events of possible drug-induced liver injury with hyperbilirubinemia (defined as aspartate aminotransferase [AST] or alanine aminotransferase [ALT] ≥3 times the upper limit of the normal range [ULN], plus either bilirubin ≥2 times the ULN or international normalized ratio [INR]>1.5) or Hy's Law events require immediate study treatment cessation and reporting as a SAE.
- Disease progression (or progressive disease) or death due to disease progression will not be considered an AE or a SAE in this study, but will be collected as an efficacy assessment.

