3.0 SELECTION OF PARTICIPANTS/ELIGIBILITY

3.1 Inclusion Criteria:

- 1. Male or female, age \geq 18 years at the time of informed consent.
- 2. Capable and willing to sign informed consent form prior to performing any protocol-related procedures.
- 3. Histologic or cytologic evidence of advanced or metastatic biliary tract cancer including cholangiocarcinoma (intra-hepatic or extra-hepatic), ampullary carcinoma, or gallbladder carcinoma.
- 4. Evidence of recurrent, locally advanced, unresectable, or metastatic disease.
- 5. Progressed following or intolerant to one or more lines of systemic therapy, or treatment-naïve subjects who either decline or being considered not a good candidate first-line systemic chemotherapy per the opinion of the treating physician
- 6. Per the opinion of the physician investigator, predicted life expectancy of >3 months.
- 7. Presence of at least 1 lesion that is measurable or evaluable using RECIST v1.1.
- 8. ECOG performance score ≤ 2 .
- 9. Per the opinion of the physician investigator, acute toxicities relating to any prior anticancer treatment have improved to Grade 1 or baseline. Exceptions include residual alopecia or Grade 2 peripheral neuropathy.
- 10. Ability to swallow capsules.
- 11. Adequate organ function, as evidenced by all of the following:

| System | Laboratory value | | |
|-------------|---------------------------------------------------------------------------------------------------------------------------------------------------------------------------------------------------------------------------|--|--|
| Hematologic | | | |
| ANC | ≥1500/µL | | |
| Platelets | ≥75,000/µL | | |
| Hemoglobin | ≥8.0 g/dL (Patients may receive erythrocyte transfusions to achieve this hemoglobin level at the discretion of the investigator. Initial treatment may not begin earlier than the day after the erythrocyte transfusion.) | | |

| System | Laboratory value | | |
|-----------------------|---------------------------------------------------------------------------------------------------------------------------------------------------|--|--|
| Hepatic | | | |
| Serum total bilirubin | ≤2 times the ULN; Patients with Gilbert's syndrome with a total bilirubin ≤3.0 times ULN and direct bilirubin within normal limits are permitted. | | |
| AST and ALT | ≤3 times the ULN, ≤ 5 times ULN for subjects with liver metastasis | | |

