7.1.6 Dosing Adjustments, Delays and Discontinuation

Abemaciclib Dose Modification for Grade 3 or 4 AEs

| Dose Level | Abemaciclib Dose |
|---------------------------|--------------------|
| Recommended starting dose | 200 mg twice daily |
| First dose reduction | 150 mg twice daily |
| Second dose reduction | 100 mg twice daily |
| Third dose reduction | 50 mg twice daily |

Complete blood counts with differentials and complete metabolic panel will be monitored every 2 weeks for the first 2 months, then monthly for the next 2 months, at the beginning of every cycle.

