| Nonhematologic Toxicity (except diarrhea and ALT increased) | Grade 3 or 4 that does not resolve with maximal supportive measures within 7 days to baseline or Grade 1 | Dose MUST be held until toxicity resolves to either baseline or ≤ Grade 1. | Dose MUST be reduced by 1 dose level. Discontinue abemaciclib for participants unable to tolerate 50 mg twice daily |
| Diarrhea | Grade 2 that does not resolve within 24 hrs to at least Grade 1 | Dose MUST be held until toxicity resolves to \(\leq \text{Grade} \) 1. | Dose MAY be reduced by 1 dose level. |
| Diarrhea | Grade 3 or 4 that does not resolve with maximal supportive measures within 7 days or requires hospitalization. | Dose MUST be held until toxicity resolves to ≤ Grade 1. | Dose must be reduced by 1 dose level - Discontinue abemaciclib for participants unable to tolerate 50 mg twice daily |

| ALT/AST increased | Grade 2 (>3.0-5.0xULN) that does not resolve within 7 days to baseline or < Grade 1 | Dose MUST be held until toxicity resolves to baseline or Grade 1 | Dose MUST be reduced by 1 dose level |
|-------------------|-------------------------------------------------------------------------------------|------------------------------------------------------------------|------------------------------------------|
| | Grade 3 (>5.0-20.0xULN) with total bilirubin >2xULN, in the absence of cholestasis | Abemaciclib therapy MUST be discontinued | Abemaciclib therapy MUST be discontinued |
| | Grade 4 (>20.0xULN) | Abemaciclib therapy MUST be discontinued | Abemaciclib therapy MUST be discontinued |

Abbreviations: ALT = alanine aminotransferase, AST=aspartate aminotransferase, ULN = upper limit of normal.

Monitor ALT, AST, and serum bilirubin prior to the start of abemaciclib therapy, every 2 weeks for the first 2 months, monthly following cycle 2, and as clinically indicated.

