7.4.3 General Guidance for Hepatic Monitoring

To ensure patient safety the investigator should collect specific recommended clinical information and follow-up laboratory tests as shown below in Table 5.

Details for hepatic monitoring depend upon the severity and persistence of observed laboratory test abnormalities. If a study patient experiences elevated ALT 5×ULN and elevated total bilirubin (TB) 2×ULN, or ALT 8×ULN, liver tests, including ALT, AST, direct bilirubin, gamma-glutamyl transferase (GGT), and creatine phosphokinase (CPK), should be repeated within 3 to 5 days to confirm the abnormality and to determine if it is increasing or decreasing. If the abnormality persists or worsens, clinical and laboratory monitoring should be initiated by the investigator, based on the hepatic monitoring tests below.

Table 5 Hepatic Monitoring Tests for a Hepatic Treatment Emergent Abnormality.

| Hepatic Hematology | Haptoglobin |
|----------------------------------|---------------------------------|
| Hemoglobin | • |
| Hematocrit | Hepatic Coagulation |
| RBC | Prothrombin Time |
| WBC | Prothrombin Time, INR |
| Neutrophils, segmented and bands | |
| Lymphocytes | Hepatic Serologies ^a |
| Monocytes | Hepatitis A antibody, total |
| Eosinophils | Hepatitis A antibody, IgM |
| Basophils | Hepatitis B surface antigen |
| Platelets | Hepatitis B surface antibody |
| | Hepatitis B Core antibody |
| Hepatic Chemistry | Hepatitis C antibody |
| Total bilirubin | Hepatitis E antibody, IgG |
| Direct bilirubin | Hepatitis E antibody, IgM |
| Alkaline phosphatase | |
| ALT | Anti-nuclear antibody |
| AST | Anti-actin antibody |
| GGT | Anti-smooth muscle antibody |
| CPK | · |

Abbreviations: ALT = alanine aminotransferase; AST = aspartate aminotransferase; CPK = creatine phosphokinase; GGT = gamma-glutamyl transferase; Ig = immunoglobulin; INR = international normalized ratio; RBC = red blood cells; WBC = white blood cells.

a Reflex/confirmation dependent on regulatory requirements and/or testing availability.

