| Dispense Abemaciclib | X | X | X | Abemaciclib is taken orally every 12 hours on days 1 through 28 of each cycle regardless of food intake. |
|------------------------------------|---|---|---|----------------------------------------------------------------------------------------------------------|
| Collection of Unused Study Drug | | X | X | |
| Study Drug Diary | | X | X | |
| Extracellular vesicles | X | | X | Every 8 weeks (±3 days) until disease progression or End of Treatment visit. |

Participants who are deriving clinical benefit after completing the treatment period may
continue on additional cycles of therapy at the discretion of the sponsor and medical monitor.
Any participant on abemaciclib after completing the treatment period will be monitored and
assessed for tumor response.

POST-TREATMENT FOLLOW-UP SCHEDULE OF ACTIVITIES

| | EOT a | Long-Term Follow-Up ^c | Instructions |
|------------------------------------------------------------------------|-------|-------------------------------------|--------------------------------------------------------------------------------------------------------------------------------|
| Physical Examination | X | | Including vital signs measurements (temperature, heart rate, respiration rate, blood pressure). |
| Weight | X | | |
| ECOG Performance Status | X | | |
| Adverse Events | X | | Only collected for unresolved AEs ≥ Grade 3 and related to the study drug. |
| Concomitant Medication | X | | |
| Collection of Unused Study Drug | X | | |
| Diagnostic Imaging –for Tumor Evaluation RECIST v.1.1 Reading | X | X | Every 3 months (± 7 days) beginning 3 months after last dose of the study drug for subjects who have not progressed. |
| Survival information | | X | Every 3 months (± 7 days) x2, beginning 3 months after last dose of the study drug then every 6 months (± 7 days) thereafter. |
| Post-Study Treatment Anti-Cancer Therapy | X | X | Every 3 months (± 7 days) x2, beginning 3 months after last dose of the study drug, then every 6 months (± 7 days) thereafter. |
| Hematology | X | | |

| Serum Chemistry | X | |
|------------------------------------|---|--|
| Coagulation Profile | X | |
| Urinalysis | X | |
| CA 19-9 | X | |
| 12-lead ECGb | X | |
| EORTC-QLQ-C30 | X | |
| Collection of Unused Study Drug | X | |
| Study Drug Diary | X | |
| Extracellular vesicles | X | |

^a End-of-treatment (EOT) visit will be completed up to 30 days (± 7 days) after last dose study drug. ^b as clinical indicated.

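### INR >1.5 is one arm of a mandatory liver stop rule, but the documents conflict on whether INR is measured during treatment

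*Combined protocol and SAP*

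**What the plan says.** Section 10.1.1 sets a rule for possible drug-induced liver injury. Its transaminase condition is "defined as aspartate aminotransferase [AST] or alanine aminotransferase [ALT] ≥3 times the upper limit of the normal range [ULN"; the second condition is "plus either bilirubin ≥2 times the ULN or international normalized ratio [INR]>1.5". Events that meet both "require immediate study treatment cessation and reporting as a SAE". INR is thus an alternative to bilirubin, not an addition to it.

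The places that govern laboratory testing are these:

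- **Section 7.2.1 (screening)** lists the clinical laboratory tests and includes PT, INR and PTT among them.
- **Section 7.2.2.1 (treatment cycles)** asks for clinical laboratory tests at C1D1, C1D15, C2D1, C2D15 and day 1 of cycles 3 to 8, without saying which ones.
- **Appendix B** has a coagulation row in the baseline table and again in the EOT column ("Coagulation Profile | X"). The table for cycles 1 to 8, which lies between them, has rows for hematology, serum chemistry and CA 19-9, and none for coagulation.
- **Section 7.1.6** names counts and chemistry only: "Complete blood counts with differentials and complete metabolic panel will be monitored every 2 weeks for the first 2 months".
- **Section 7.3.8** names three liver tests: "Monitor ALT, AST, and serum bilirubin prior to the start of abemaciclib therapy", and then at intervals on treatment.
- **Section 7.4.3** starts a work-up as follows: "If a study patient experiences elevated ALT 5×ULN and elevated total bilirubin (TB) 2×ULN, or ALT 8×ULN, liver tests" are repeated within 3 to 5 days. The repeat panel has no INR. INR appears in Table 5, which is reached only if the abnormality persists or worsens.

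On entry, inclusion criterion 11 in section 3.1 allows AST and ALT "≤3 times the ULN, ≤ 5 times ULN for subjects with liver metastasis" and sets no INR limit.

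**The concern.** A mandatory stop works only if its inputs are measured. Bilirubin is scheduled throughout treatment; INR is scheduled on treatment under one reading of the body text and not under Appendix B. Section 7.2 refers the reader to Appendix B for study procedures, so a site could follow that table in good faith and never draw an INR between baseline and end of treatment. An INR at the EOT visit, which may fall up to 30 (±7) days after the last dose, comes too late to trigger cessation.

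At stake is a participant with raised transaminases, bilirubin below 2×ULN and a rising INR. Section 10.1.1 says this participant must stop. Under Appendix B nothing scheduled would show that the rule had been met. Two sites, or two coordinators at one site, could also apply the same rule to different data, which would make the liver-related SAE count depend on which section was followed.

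**Working it through.** The plan gives no figure to reproduce. The check sets the thresholds side by side, in multiples of ULN, reading the 5× and 8× in 7.4.3 as at or above those values.

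**Inputs**

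- Stop rule (10.1.1): (AST or ALT ≥3) and (bilirubin ≥2 or INR >1.5).
- Work-up trigger (7.4.3): (ALT ≥5 and bilirubin ≥2) or ALT ≥8. There is no AST trigger.
- On-treatment INR under Appendix B: none scheduled.

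**Step 1: where INR alone decides the rule.** If bilirubin is ≥2, the second condition is already met and INR changes nothing. INR is decisive only when AST or ALT is ≥3 and bilirubin is <2.

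**Step 2: which part of that region 7.4.3 reaches.** The first branch needs bilirubin ≥2, so it never falls in the region from step 1. The second branch starts at ALT 8.

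| Finding on treatment, bilirubin <2×ULN | INR arm decisive under 10.1.1? | INR called for by Appendix B or 7.4.3? |
|---|---|---|
| ALT 3 to <8×ULN | Yes | No |
| ALT ≥8×ULN | Yes | Only via Table 5, after a repeat at 3 to 5 days shows persistence or worsening |
| AST ≥3×ULN, ALT not raised | Yes | No, at any AST level |

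A grid of ALT from 1 to 12×ULN and bilirubin from 0.5 to 4×ULN, in steps of 0.1, gives the same boundary: INR is decisive from ALT 3.0, 7.4.3 does not reach it from 3.0 to 7.9, and reaches it from 8.0.

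**Step 3: the other reading.** If the laboratory tests in 7.2.2.1 carry the full content listed in 7.2.1, INR is drawn at every treatment visit and the gap closes. Nothing in the documents says which of 7.2.2.1 and Appendix B prevails.

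**Step 4: entry values (secondary).** Inclusion 11 overlaps the transaminase condition. With liver metastasis, AST or ALT from 3 to 5×ULN is both eligible and at or above the 10.1.1 threshold. Without liver metastasis the overlap is the single value 3×ULN. Section 10.1.1 gives no baseline-adjusted threshold.

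**The case against.** **The rule can still operate.** The best reply is that the body text already requires INR. Section 7.2.3 uses the same general term for the EOT visit, and there Appendix B does list coagulation, so the term can include it. INR may also be ordered on clinical judgement, and 7.4.3 reaches it at a confirmed ALT of 8×ULN. This stands. A reader might infer that the INR arm can never fire on treatment; the documents do not support that. They support a conflict that leaves the measurement unassured.

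**Other controls cover part of the gap.** Section 7.3.8 requires the dose to be held and reduced for a Grade 2 rise in ALT or AST (>3.0 to 5.0×ULN) that does not resolve within 7 days, whatever the INR, and discontinuation at Grade 4 (>20.0×ULN). This also stands, and it lowers the stakes. It does not replace the rule: a hold with dose reduction is not immediate cessation with an SAE report. In the table as it can be read, the Grade 3 row (>5.0 to 20.0×ULN) applies only with bilirubin above 2×ULN.

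**Abnormal values at entry.** A reader might infer that a participant with liver metastasis, eligible at 4×ULN and with an INR above 1.5, would automatically produce a stop and an SAE from the pre-treatment state. The documents do not support that. The rule concerns possible drug-induced injury, section 10.1.1 defines an AE as something that develops or worsens during the study, and section 10.1.2 records events before first dosing as medical history. What remains is that 10.1.1 is silent on how its numbers apply to values already raised at entry.

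**Frequency.** The MONARCH 1 laboratory table gives rates of raised ALT and AST. A reader might turn them into a chance of a missed stop. They cannot serve for this: Grade 3 includes values above 8×ULN and values with raised bilirubin, and the documents give no rate for INR.

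**Conclusion.** The concern holds as a conflict between sections on an input to a mandatory safety stop. Under Appendix B with 7.4.3, INR is not called for when ALT is 3 to <8×ULN with bilirubin below 2×ULN, or when AST alone is raised. Under the broad reading of 7.2.1 and 7.2.2.1 it is. The conclusion rests on two readings: that the absent coagulation row in the cycle 1 to 8 table is how sites would see it, and that the 7.4.3 multiples mean at or above. How many participants would be affected is unknown. The silence on raised transaminases at entry is a secondary point, material mainly for participants with liver metastasis. The correction is worth making because it concerns patient safety and is inexpensive; it does not show that the stop rule has failed as a whole.

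**What to change.** Reconcile sections 10.1.1, 7.2.2.1, 7.3.8 and 7.4.3 with Appendix B so that the on-treatment schedule measures every input the stop rule uses, and so that the body text and the appendix name the same tests at the same visits. State in 7.2.2.1 which laboratory tests are meant. The timing of INR and all thresholds are for the sponsor to decide.

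As a secondary edit, reconcile 10.1.1 with inclusion 11, so that it is clear how the rule's numbers apply to participants with liver metastasis who enter with AST or ALT of 3 to 5×ULN.

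The cost is a short text amendment and a few INR tests at blood draws that already take place. Sample size, endpoints and efficacy analyses are unaffected.

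### The dosing table in 7.3.8 has no instruction for Grade 3 ALT without bilirubin above 2×ULN, and its ALT/AST rows omit the liver stopping rule in 10.1.1

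*Combined protocol and SAP*

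**What the plan says.** **Dosing table (7.3.8).** The ALT/AST block has three rows.
- The first covers "Grade 2 (>3.0-5.0xULN) that does not resolve within 7 days to baseline" or below Grade 1. The action is "Dose MUST be held until toxicity resolves to baseline or Grade 1", followed by a mandatory reduction of one level. The row sets no bilirubin or INR condition.
- The second covers "Grade 3 (>5.0-20.0xULN) with total bilirubin >2xULN, in the absence of cholestasis": discontinue.
- The third covers Grade 4 (>20×ULN): discontinue.

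The general rows are labelled "Nonhematologic Toxicity (except diarrhea and ALT increased". One of them covers "Grade 3 or 4 that does not resolve with maximal supportive measures within 7 days to baseline or Grade 1", with a hold and a one-level reduction. Section 7.3.8 closes by requiring ALT, AST and bilirubin before treatment, every 2 weeks for 2 months, monthly after cycle 2, and as clinically indicated.

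**Liver stopping rule (10.1.1).** For possible drug-induced liver injury with AST or ALT at least 3×ULN, "plus either bilirubin ≥2 times the ULN or international normalized ratio [INR]>1.5", such "events require immediate study treatment cessation and reporting as a SAE". This stands in the definition of an adverse event, not in the dosing section. It does not say whether cessation is permanent.

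**Hepatic monitoring (7.4.3).** Repeat liver tests within 3 to 5 days are triggered by "elevated ALT 5×ULN and elevated total bilirubin (TB) 2×ULN, or ALT 8×ULN". If the abnormality persists or worsens, further monitoring follows. No dosing instruction is given.

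**Other relevant places.** Section 7.1.6 is headed for Grade 3 or 4 events but lists only dose levels. Section 3.4 withdraws a participant for toxicity judged unacceptable, or for possibly related toxicity unresolved at 14 days. Section 7.4.5 has its own ILD/pneumonitis table (discontinue at Grade 3 or 4), and its general nonhematologic table excludes diarrhea, ALT and ILD/pneumonitis.

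**The concern.** The rules for ALT run the wrong way. Persistent Grade 2 ALT must be held, while the more severe isolated Grade 3 rise has no instruction. The dosing table also leaves out the protocol's own liver stopping rule, although that rule determines whether treatment continues at all.

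An investigator looking at a liver result would naturally turn to 7.3.8. For one range of values it gives no answer. For another it gives a slower and milder answer than 10.1.1. The stakes are patient safety and consistent discontinuation decisions. The background section reports two deaths from hepatotoxicity among patients on abemaciclib plus fulvestrant in MONARCH 2. Eligibility (3.1) admits bilirubin up to 2×ULN, and AST/ALT up to 5×ULN with liver metastases, so some participants start close to these thresholds.

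**Working it through.** No sample size or test is involved. The check sets the rules side by side for each range of values. The 10.1.1 column applies when the event is judged possible drug-induced liver injury.

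| ALT | Companion finding | 7.3.8 ALT/AST rows | 10.1.1 |
|---|---|---|---|
| >3-5×ULN | bilirubin <2×ULN and INR ≤1.5 | if unresolved within 7 days: hold, reduce one level | not met |
| >3-5×ULN | bilirubin ≥2×ULN or INR >1.5 | same row, same 7-day wait | stop at once, SAE |
| >5-20×ULN | bilirubin <2×ULN and INR ≤1.5 | **no row** | not met |
| >5-20×ULN | bilirubin exactly 2×ULN, or INR >1.5 with bilirubin ≤2×ULN | **no row** | stop at once, SAE |
| >5-20×ULN | bilirubin >2×ULN, no cholestasis | discontinue | stop at once, SAE |
| >5-20×ULN | bilirubin >2×ULN, cholestasis | **no row** | stop at once, SAE |
| >20×ULN | any | discontinue | depends on bilirubin/INR |

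**Can another section fill the third line (isolated Grade 3 ALT)?**
- General nonhematologic rows in 7.3.8 and 7.4.5: no, both exclude ALT. Isolated Grade 3 AST could still fall under them, since only ALT is named in the exclusion.
- 7.1.6: it gives the reduction ladder, with no trigger for using it.
- 7.4.3: repeat tests only. With bilirubin below 2×ULN the trigger is ALT 8×ULN. ALT >5 to <8×ULN with bilirubin <2×ULN therefore has neither a dosing row nor a 7.4.3 trigger.
- Routine tests in 7.3.8: every 2 weeks, then monthly. These detect the event but do not direct the dose.
- 3.4: investigator judgement, and withdrawal at 14 days.

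**Exposure while no rule acts**, at 200 mg twice daily (7.1.5): doses = 2 × days, and mg = 200 × doses.
- Repeat tests under 7.4.3: 3-5 days = 6-10 doses = 1,200-2,000 mg.
- Wait in the Grade 2 row: 7 days = 14 doses = 2,800 mg.
- Limit in 3.4: 14 days = 28 doses = 5,600 mg.

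These are upper bounds. They assume full dose and an investigator who does not act sooner.

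**Example for the second defect.** Entry values are normal. At cycle 1 day 15, ALT is 4×ULN and bilirubin 2.5×ULN, judged possible drug-induced injury. Under 10.1.1 treatment stops that day. Under the 7.3.8 row read alone, dosing may run up to 7 more days (14 doses, 2,800 mg), followed by a hold and a reduction to 150 mg twice daily.

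**How often Grade 3 ALT of any kind might be seen.** The protocol reports 3% in MONARCH 1 (Table 4; 200 mg twice daily alone) and 4% in MONARCH 2 (Table 2; 150 mg plus fulvestrant). Assuming those breast-cancer rates, the chance of at least one case is 1 − (1 − p)^n:
- n = 10: 1 − 0.97^10 = 26.3%; 1 − 0.96^10 = 33.5%.
- n = 20: 1 − 0.97^20 = 45.6%; 1 − 0.96^20 = 55.8%.

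The documents do not split these events by bilirubin and give no rate in biliary cancer.

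**ILD/pneumonitis.** For persistent Grade 2 the two sections agree. At Grade 3 or 4 the 7.3.8 general row, whose label does not exclude ILD, gives hold and reduce if unresolved within 7 days; the 7.4.5 ILD table says discontinue.

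**The case against.** The strongest defence concerns the stopping rule. Section 10.1.1 is specific and mandatory. Section 7.3.8 introduces its modifications as recommended, says nothing about continuing when bilirubin is raised, and does not forbid an earlier stop. Obeying 10.1.1 breaches nothing in 7.3.8. That stands. A reader might infer that the protocol makes investigators keep dosing through a suspected liver injury; the text does not support that. What is missing is the rule, or a pointer to it, in the dosing section.

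On ILD, the defence is stronger still. A reader might infer that Grade 3 or 4 pneumonitis could properly be managed by dose reduction. The dedicated 7.4.5 table says discontinue, and the adjoining table excludes ILD/pneumonitis by name, so the intent is clear. Only a label mismatch remains.

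On Grade 3 ALT, it can be said that routine liver tests continue, that investigators may always hold or withdraw treatment, and that with INR >1.5 the rule in 10.1.1 already applies to possible drug-induced injury. All true, but none of this is a dosing instruction for the isolated rise.

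A reader might also take the 26-56% range as the frequency of the gap. It is not. It covers any Grade 3 ALT, including cases with bilirubin >2×ULN that 7.3.8 does address, and it borrows rates from breast cancer. How often the gap itself would be met cannot be estimated from the documents.

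**Conclusion.** The main defect holds as written: Grade 3 ALT without bilirubin above 2×ULN has no dosing instruction, although persistent Grade 2 ALT must be held and reduced. The gap is widest at ALT >5 to <8×ULN with bilirubin <2×ULN and INR ≤1.5, where the only fixed limit is the 14-day rule (at most 28 doses, 5,600 mg).

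The second defect is an omission. The 7.3.8 ALT/AST rows do not carry the 10.1.1 rule. Read alone, they are laxer for possible drug-induced injury at >3-5×ULN with bilirubin ≥2×ULN or INR >1.5, and at >5-20×ULN with INR >1.5 or bilirubin exactly 2×ULN. Grade 3 with bilirubin >2×ULN and cholestasis also lacks a row, but 10.1.1 stops it if judged possible drug-induced injury. The ILD label is minor.

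The conclusion rests on the text of the tables; the exposure figures rest on full dosing and no earlier action. Response rate, SAE classification (set by 10.1.1) and the stated analyses are untouched. On safety grounds this should be fixed.

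**What to change.** 1. In 7.3.8, state that an event meeting the 10.1.1 criterion and judged possible drug-induced liver injury overrides the ALT/AST rows: stop at once and report as an SAE. Say whether the stop is permanent. Say how participants who enter with raised AST/ALT or bilirubin are judged against baseline, since 3.1 admits values that can already reach the numeric threshold.
2. Add a row for Grade 3 ALT/AST not meeting 10.1.1: hold until baseline or Grade 1, then reduce one level. This extends the existing Grade 2 action without its 7-day wait.
3. Relabel the 7.3.8 nonhematologic rows to exclude diarrhea, ALT/AST increased and ILD/pneumonitis, with a pointer to 7.4.5 for ILD.

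Cost: one amendment at a single center, and possibly a few more dose holds. No visits or scheduled tests need be added. The INR limb has a limit: Appendix B schedules coagulation only at baseline and end of treatment, so on treatment it relies on tests done when clinically indicated.
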